6.3 Treatments Administered

In Part 1 (dose-escalation), each patient will be assigned a dose level as described in [Section 4.1.1](#). In Part 2 (expansion), all patients will be assigned to the dose level identified in Part 1 by the DESC.

Patients will receive a 1-hour IV infusion of ADCT-301 on Day 1 of Cycle 1. If ADCT-301 is well tolerated after the first infusion, the infusion duration may be shortened to a 30-minute IV infusion for subsequent cycles, on an individual patient basis, at the Investigator's discretion. Variations in infusion times due to minor differences in IV bag overfill/underfill and the institution's procedure for flushing chemotherapy lines will not result in protocol deviation.

Prophylactic antiemetic medications, electrolyte supplementation, and other standard supportive care measures may also be administered according to standard treatment center protocols, or as in [Section 6.2](#).

Because of non-clinical observations related to nephropathy and adrenal gland changes, adequate patient hydration (e.g., 8 to 10 glasses of water or equivalent per day) is recommended for patients receiving ADCT-301.

Available pre-clinical data on ADCT-301 does not suggest a photosensitivity concern, based on the lack of any signals in the rat and monkey toxicology studies with ADCT-301 and the non-clinical experience with SG3199, including a QWBA (quantitative whole-body autoradiography) study indicating no specific accumulation to melanin containing tissues, skin or eyes.

However, skin rash has been reported in the ADCT-301 program, as well as with another investigational agent containing the same pyrrollobenzodiazepine warhead.²⁸ The rash has been limited to areas at risk for sun exposure; it is therefore recommended that precautions are taken to avoid prolonged exposure of skin to direct sunlight.

6.4 Dose Delays and Modifications

Patients will receive the first 2 cycles, irrespective of blood count recovery. For patients achieving a CR/CRi, the subsequent cycle would be delayed until peripheral blood count recovery (absolute neutrophil count [ANC] $>0.5 \times 10^9/L$ and/or platelets $>50 \times 10^9/L$).

The Investigator should suspend ADCT-301 dosing for up to 21 days for any patient who experiences a protocol-defined DLT during any treatment cycle. At the discretion of the Investigator, the dose may also be delayed for up to 21 days for any toxicity that does not meet DLT criteria. Resumption of dosing with ADCT-301 after suspension is at the discretion of the Investigator, based on assessment of the patient's clinical condition and whether or not the patient is deriving potential clinical benefit from treatment with ADCT-301. Following recovery to CTCAE Grade 1 or to baseline grade, treatment with ADCT-301 may resume at the Investigator's discretion.

Patients who resume treatment following a dose delay may, at the discretion of the Investigator, have their dose reduced by 1 dose level. If toxicity recurs at a severity that would mandate a dose delay, then the dose may be further reduced 1 dose level. If toxicity recurs at such level, then the patient is to be discontinued from treatment. Dose re-escalation is allowed at the Investigator's discretion, at maximum to the dose level the patient was initially assigned to.

Dosing frequency may be adjusted according to individual patient response as described in [Section 4.1.1](#).

Patients experiencing certain types of infection during the course of participation in this clinical study also must delay further dosing, as stipulated in [Section 7.3.4.5](#).

Patients experiencing any autoimmune toxicities (e.g., endocrinopathies) \geq grade 1 need to be followed at least weekly to quickly detect deterioration and modify dosing as per DLT criteria (can be done by telephone unless symptoms worsen).

Patients who experience a DLT ([Section 7.3.1.1](#)) during Cycle 1 are to be permanently withdrawn from the study. Patients who experience the following significant toxicities will be immediately and permanently withdrawn from treatment with ADCT-301:

- Any patient who experiences a CTCAE Grade 3 or higher hypersensitivity reaction, regardless of premedication, during any cycle of treatment ([Appendix 13.2](#)).
- Any patient who experiences a recurrent CTCAE Grade 3 or 4 toxicity, excluding hematological toxicity.
- Any patient who requires a dosing delay >21 consecutive days from the planned Day 1 dosing at any time during treatment (except in case of potential patient benefit, which must be approved by the Sponsor).

Neurological toxicities: dose delay/permanent discontinuation

Patients experiencing any new neurological toxicities \geq Grade 1, not explained by previous medical history, that could be linked to or may be an early indicator of polyradiculopathy/GBS, such as ascending (bilateral) sensory loss or motor weakness, need to be immediately evaluated by a neurologist and dosing of ADCT-301 needs to be delayed until polyradiculopathy/GBS is ruled out. Should further clinical, radiologic, or laboratory evidence support the diagnosis of polyradiculopathy/GBS with the level 1 of diagnostic certainty ([Appendix 13.3](#)), treatment with ADCT-301 must be stopped and patient must be permanently discontinued.

Patients with Grade \geq 3 neurologic toxicities, defined as peripheral sensory and peripherally motor neuropathies, must be permanently discontinued.

Other new neurological findings not explained by previous medical history increase of \geq 1 grade over baseline will result in dose delay; dosing may be resumed after resolution to baseline, at the investigator's discretion. The patient must be carefully monitored at least weekly until such resolution (can be done by telephone unless symptoms worsen).

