7.3.1 Dose-Limiting Toxicities and Dose-Escalation Scheme

7.3.1.1 Definition of Dose-Limiting Toxicities

A DLT is defined as any of the following events, except those that are clearly due to underlying disease or extraneous causes:

- A hematologic DLT is defined as:
 - Grade 3 or higher event of neutropenia and/or thrombocytopenia or a Grade 4 anemia, with a hypocellular bone marrow lasting for 6 weeks or more after the start of a cycle, in the absence of residual leukemia (i.e., with <5% blasts). In case of a normocellular bone marrow with <5% blasts, 8 weeks with \geq Grade 3 pancytopenia will be considered a DLT.
- A non-hematologic DLT is defined as:
 - Grade 4 tumor lysis syndrome (Grade 3 TLS will not constitute DLT unless it leads to irreversible end-organ damage).
 - Grade 3 or higher AEs (including nausea, vomiting, diarrhea, and electrolyte imbalances lasting more than 48 hours despite optimal therapy; excluding all grades of alopecia).
 - Grade 3 or higher hypersensitivity reaction (regardless of premedication).
 - Grade 3 or higher skin ulceration.
 - Peripheral sensory or motor neuropathy \geq Grade 2.

Note: The DLT observation period for dose-escalation will be 1 cycle. Patients who experience a DLT during Cycle 1 are to be permanently discontinued from the study.

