4.2 Subject Disposition

For the Safety analysis set, the number and percentage of subjects who discontinued study treatment and discontinued the study for each reason will be tabulated for each dose level.

Subject disposition data will be listed.

The number and percentage of patients with any important clinical study report (CSR) reportable protocol deviation will be summarized overall and by type of deviation. The pre-defined important CSR reportable protocol deviations are listed below; in addition, any other protocol deviations deemed by ADCT medical to be important CSR reportable deviations will be included in the summary.

1. Patient entered the study even though they did not satisfy the entry criteria
2. Patient received an excluded concomitant treatment
3. Patients who developed withdrawal criteria during the study but were not withdrawn.
The withdrawal criteria include:
 - Grade 3 or higher hypersensitivity reaction
 - a recurrent Grade 3 or 4 toxicity, excluding hematological toxicity
 - a protocol-defined dose-limiting toxicity (DLT) during Cycle 1

- a dosing delay >21 (except in case of potential patient benefit, which must be approved by the Sponsor) or
 - diagnosis of polyradiculopathy/GBS with the level 1 of diagnostic certainty
 - Grade ≥ 3 neurologic toxicities, defined as peripheral sensory and peripherally motor neuropathies
4. toxicity recurs at the 2nd reduced dose level and at a severity that would mandate a treatment withdrawal Patient who received the wrong treatment or incorrect dose. For example,
- actual dose of study drug was more than 15% greater than protocol defined planned dose level
 - patient started next cycle less than 18 days later after Day 1 of the most recent treatment cycle

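### When a non-hematologic Grade 3-4 DLT first seen after Cycle 1 recurs at a reduced dose, Section 6.4 both permits a second reduction and orders permanent withdrawal

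*Protocol*

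**What the plan says.** Protocol Section 6.4 sets out a stepwise rule for delays and reductions.

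- Delay: "The Investigator should suspend ADCT-301 dosing for up to 21 days for any patient who experiences a protocol-defined DLT during any treatment cycle". Section 7.3.1.1 defines non-hematologic DLTs mainly by "Grade 3 or higher AEs (including nausea, vomiting, diarrhea, and electrolyte imbalances lasting more than 48 hours despite optimal therapy", with some separate items.
- First reduction: "Patients who resume treatment following a dose delay may, at the discretion of the Investigator, have their dose reduced by 1 dose level".
- Second reduction: "If toxicity recurs at a severity that would mandate a dose delay, then the dose may be further reduced 1 dose level".
- End of the ladder: "If toxicity recurs at such level, then the patient is to be discontinued from treatment".

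Further down, the same section lists toxicities for which the patient is to leave treatment at once and for good. One entry reads: "Any patient who experiences a recurrent CTCAE Grade 3 or 4 toxicity, excluding hematological toxicity".

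SAP Section 4.2 pre-defines the important deviations for the clinical study report. One category is a patient who met a withdrawal criterion and was not withdrawn. Its criteria include "a recurrent Grade 3 or 4 toxicity, excluding hematological toxicity". The list also refers to the end of the ladder: "toxicity recurs at the 2nd reduced dose level and at a severity that would mandate a treatment withdrawal". That line runs straight into the separate item on wrong treatment or incorrect dose.

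**The concern.** An investigator whose patient has a second Grade 3 episode at the first reduced level finds two instructions in one section. One allows a further step down; the other ends treatment. Sites could handle the same event differently, and the choice decides whether a patient with a recurrent severe toxicity is given the drug again. Safety and tolerability are primary objectives, so the handling of such events bears on the trial's main output.

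It also affects the reporting. SAP 4.2 would count a site that used the ladder as having an important deviation, although the protocol's own text allows the step. The number of patients with a TEAE leading to permanent discontinuation, the exposure summaries (number of infusions, cumulative dose, relative dose intensity) and the deviation table all depend on which instruction was followed.

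**Working it through.** No figure in the plan bears on this point, so the check is to apply both rules to one case and then find the limits of the overlap.

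**Test case.** A patient has a non-hematologic Grade 3 DLT in Cycle 2, other than hypersensitivity or peripheral neuropathy. Dosing is delayed, the patient recovers and restarts one level lower, and the same event returns at Grade 3.

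1. Delay severity: the event is a DLT, and Section 6.4 ties suspension to a DLT in any cycle. The recurrence is therefore at a severity that calls for a delay.
2. Ladder: one further level down is permitted. Discontinuation follows only if toxicity recurs at that second reduced level.
3. Withdrawal list: the recurrence is non-hematologic and Grade 3, so withdrawal is required now.
4. SAP 4.2: if the patient stays on treatment, a listed withdrawal criterion was met without withdrawal, which is an important deviation.

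At the same recurrence, one rule allows no further dose. The other allows treatment at a second reduced level with no stated limit on cycles. Section 6.4 also allows re-escalation up to the assigned level, at the investigator's discretion.

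**Limits of the overlap.**

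| Event | Ladder | Withdrawal list or other rule | Conflict |
|---|---|---|---|
| DLT in Cycle 1 | not reached | withdrawn at first occurrence | no |
| Hypersensitivity, Grade 3 or higher | not reached | withdrawn at first occurrence | no |
| Peripheral neuropathy, Grade 3 or higher | not reached | discontinued at first occurrence | no |
| Hematologic DLT | applies | excluded from the recurrence entry | no |
| Grade 2 peripheral neuropathy | applies | below Grade 3 | no |
| Listed infections and other new neurological findings, below Grade 3 | applies | below Grade 3 | no |
| Other non-hematologic Grade 3-4 DLT after Cycle 1, recurring at Grade 3-4 after a first reduction | second reduction permitted | withdrawal required | **yes** |

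The protocol does not define what counts as recurrent. The test case uses the same event at Grade 3 both times, which meets either a narrow or a broad sense. A Grade 2 event delayed at discretion that returns at Grade 3 is left out, because it is arguably not yet a recurrent Grade 3 toxicity.

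**SAP line on the second reduced level.** The protocol's step at that level states no explicit severity. The SAP adds one, defined by whether the event would mandate withdrawal, and the line is merged with the wrong-dose item. As printed it does not match the protocol step.

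**The case against.** The strongest reply is that the rules are not truly opposed. The ladder is permissive and the list is mandatory, so a site that withdraws satisfies both. On that reading the list simply limits the ladder, which keeps real work to do for hematologic DLTs, Grade 2 neuropathy, infections and other neurological findings. This is a possible reading, and its first part stands: withdrawal breaches neither rule. But the protocol does not state it. The ladder refers to toxicity without limit and carries no cross-reference, while the section writes exceptions elsewhere when it intends them, such as the carve-out for hematological events. The reading would also take the ladder away from most of the DLT events that trigger a delay.

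A second reply is that the suspension sentence is worded as a recommendation, so a DLT does not strictly mandate a delay. It is nevertheless the section's main rule on delay.

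A third is that existing oversight limits silent divergence. Investigators confer with the sponsor on serious or intolerable events (Section 5.2.2), and the DESC reviews safety at least monthly (Section 7.3.1.2). That lowers the risk but does not say which instruction applies.

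A fourth concerns the effect on outputs, and it stands in part. The SAP overview pools delay, reduction and interruption. The patient in the test case is already in that count after the first delay, so that patient count does not change. Efficacy data are listed only, and no hypothesis testing is planned.

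A reader might also infer that the SAP replaced the protocol's delay wording with withdrawal wording at the second reduced level. The documents do not support that. The delay wording qualifies the recurrence before the second reduction, and the protocol gives no explicit severity at the level after it. The accurate statement is that the SAP adds a qualifier.

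**Conclusion.** The inconsistency is real and narrow. It covers non-hematologic Grade 3-4 toxicities that meet DLT criteria after Cycle 1, are not hypersensitivity or peripheral neuropathy, lead to a delay and a one-level reduction, and recur at Grade 3-4. For these, Section 6.4 gives incompatible instructions with no stated precedence, and SAP 4.2 classes use of the permitted reduction as an important deviation.

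Two stronger readings are tempting. One is that the second reduction conflicts with the withdrawal list for every non-hematologic Grade 3-4 event. It does not, because several such events are withdrawn at first occurrence and never reach the ladder. The other is that patients were in fact handled inconsistently. Nothing in the documents shows that any patient met this scenario, so the number affected is unknown and may be zero.

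The conclusion assumes that a DLT is a delay-mandating severity and that the return of the same toxicity is recurrent. The trial was terminated before dose escalation was complete (SAP Section 3.3), which limits the value of a protocol amendment. The classification of deviations for the report still depends on resolving the point.

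**What to change.** - **Protocol Section 6.4:** reconcile the ladder and the withdrawal list so that no event falls under both, and cross-refer the two. The sponsor's medical team decides which rule governs; this review does not.
- **SAP Section 4.2:** align the withdrawal criteria with the reconciled text. Separate the line on the second reduced level from the wrong-dose item, and match its severity wording to the protocol.
- **If no amendment is feasible:** state in the SAP which reading governs deviation classification, and report any patient who continued dosing after such a recurrence, even if there are none.

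The cost is a clarifying paragraph in the protocol, a short correction in SAP 4.2 and a check of data already collected. No extra patients or procedures are needed.

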6.5 Study Stopping Rules

The study will be stopped if any of the following circumstances occur:

- Two additional patients (from date of December 14, 2017) develop polyradiculopathy/GBS (Level 1 of diagnostic certainty; [Appendix 13.3](#)). Continuation of patients who have shown clinical benefit will be discussed with the relevant regulatory authority(ies) if this stopping rule is applied.
- \geq 30% of patients experience a specific Grade 4 or higher non-hematologic treatment-emergent AE.

Furthermore, patient enrollment will be halted, pending a safety analysis and review with the relevant regulatory authority(ies):

- if any patient in Part 1 or Part 2 experiences a CTCAE Grade 5 AE, or 2 non-hematologic CTCAE Grade 4 AEs, which is not attributable to the underlying disease, and for which relationship to ADCT-301 cannot be ruled out, within 30 days of their last dose of ADCT-301.
- in the event of another single case of GBS. Patients currently on trial having clinical benefit or not yet having reached first bone marrow assessment can continue on study once informed and they consent to continue treatment.

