Dose-escalation (Part 1) will be conducted according to a 3+3 design. The initial dose of ADCT-301 will be 3 µg/kg (Dose Level 1), and the highest allowed dose will be 150 µg/kg every three weeks (50 µg/kg every week). The DLT observation period for dose-escalation will be 1 cycle. The first patient at each new dose level must be observed for 7 days for occurrence of AEs prior to treating the second patient at that dose level. Patients will be entered sequentially to each dose level.

For each dose level, if none of the first 3 patients at that level experiences a DLT, new patients may be entered at the next higher dose level. If 1 of 3 patients experiences a DLT, up to 3 more patients are to be treated at that same dose level. If none of the additional 3 patients at that dose level experiences a DLT, new patients may then be entered at the next higher dose level. However, if 1 or more of the additional 3 patients experience a DLT, then no further patients are to be started at that dose level and the preceding dose is identified as the MTD. The MTD; therefore, is defined as the highest dose level at which none of the first 3 treated patients, or no more than 1 of the first 6 treated patients, experiences a DLT.

No intra-patient dose-escalation is allowed.

The number of dose levels will depend on the emergent toxicity profile of ADCT-301 and will be decided by the DESC; PK and PD evaluations may also inform decision making.

During Part 1 (dose-escalation), the DESC may expand enrollment at doses below the current dose level as part of the dose-escalation process.

No more than 9 additional patients (e.g., 3 cohorts of 3 patients) will be enrolled in the remaining dose escalation portion of this study (max. dose level 50 µg/kg/week) from the date of protocol amendment number 5, unless 2 additional patients attain a PR, CR or CRi, in which case additional patients will be treated at a dose patients have cleared the DLT period, to determine if there is sufficient evidence of clinical activity to continue the study.

Additional patients may only be added at a lower dose level provided there is at least 1 patient who has achieved a PR or better ([Section 7.1](#)). No more than 10 patients in total can be treated at any dose level unless ≥ 3 of the 10 patients have achieved a PR or better.

Every 3-Week Administration

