4.1.1 Dose-escalation (Part 1) and Determination of Maximum Tolerated Dose

Dose-escalation will be conducted according to a 3+3 design (Figure 2). The initial dose of ADCT-301 will be 3 µg/kg (Dose Level 1), and the highest allowed dose will be 150 µg/kg every three weeks (50 µg/kg every week).

The DLT (see Section 7.3.1.1 for further details) observation period for dose-escalation will be 1 cycle. The first patient at each new dose level must be observed for 7 days for occurrence of AEs prior to treating the second patient at that dose level. Patients will be entered sequentially to each dose level.

For each dose level, if none of the first 3 patients at that level experiences a DLT, new patients may be entered at the next higher dose level. If 1 of 3 patients experiences a DLT, up to 3 more patients are to be treated at that same dose level. If none of the additional 3 patients at that dose level experiences a DLT, new patients may then be entered at the next higher dose level. However, if 1 or more of the additional 3 patients experiences a DLT, then no further patients are to be started at that dose level and the preceding dose is identified as the MTD. The MTD, therefore, is defined as the highest dose level at which none of the first 3 treated patients, or no more than 1 of the first 6 treated patients, experiences a DLT.

No intra-patient dose-escalation is allowed.

[figure not shown]

Figure 2. Schematic Representation for Dose-escalation (3+3) Design

* For every 3 weeks (Q3W) administration, the dose increase will never exceed 100% or 20 µg/kg at dose levels below 100 µg/kg and 50 µg/kg for dose levels between 100 and 150 µg/kg, whichever is less. Dose adjustment for other treatment schedules, such as QW dosing are included below. Abbreviations: DLT, dose-limiting toxicity; MTD, maximum tolerated dose; <, less than; ≥ greater than or equal to.

The number of dose levels will depend on the emergent toxicity profile of ADCT-301 and will be decided by the DESC ([Section 7.3.1.2](#)); PK and PD evaluations may also inform decision making.

During Part 1 (dose-escalation), the DESC may expand enrollment at doses below the current dose level as part of the dose-escalation process. Additional patients may only be added at a lower dose level provided there is at least 1 patient who has achieved a PR or better ([Section 7.1](#)).

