No more than 9 additional patients (e.g., 3 cohorts of 3 patients) will be enrolled in the remaining dose escalation portion of this study (max. dose level 50 µg/kg/week) from the date of protocol amendment number 5, unless 2 additional patients attain a PR, CR, or CRi, in which case additional patients will be treated at a dose patients have cleared the DLT period, to determine if there is sufficient evidence of clinical activity to continue the study.

No more than 10 patients in total can be treated at any dose level unless ≥ 3 of the 10 patients have achieved a PR or better.

Every 3-Week Administration

Patients will be given ADCT-301 on Day 1 of each 3-week treatment cycle.

When the dose is escalated, the dose may increase by 100% if no DLTs are observed at the current level (e.g., at 6 µg/kg, the dose increase is 6 µg/kg). Once a DLT is observed at a given dose level, the next dose may only increase by 50% (e.g., at 6 µg/kg, the dose increase is 3 µg/kg). The dose may never increase by more than 100%, or more than an absolute value of 20 µg/kg at dose levels below 100 µg/kg and 50 µg/kg for dose levels between 100 and 150 µg/kg, whichever is less.

Weekly Administration

Patients will be given ADCT-301 (QW) on Days 1, 8, and 15 of each 3-week treatment cycle.

The first dose level for the QW dosing will be based on the safety and tolerability of patients who have been treated on the Q3W schedule. The first 3 patients will be given a cumulative dose each cycle that is comparable to (but not higher than) the highest dose tested at the Q3W dose schedule at which 3 patients completed the DLT observation period without a DLT. For example, if the highest Q3W dose tested at which 3 patients did not experience a DLT was cohort 92 µg/kg, the first cohort to receive (QW) dosing will receive 30 µg/kg each week for 3 weeks.

When the dose is escalated, the dose may increase by 50% if no DLTs are observed at the current level. Once a DLT is observed at a given dose level, the next dose may only increase by 25%. The dose may never increase by more than 50%, or more than an absolute value of 20 µg/kg/week, whichever is less.

A patient will maintain the same treatment schedule throughout the duration of the trial.

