4.1.2 Dose Expansion (Part 2)

During Part 2 (dose expansion), patients will be monitored for safety using the same DLT criteria employed during Part 1 (dose-escalation). If during the treatment period, >30% of patients experience safety events that would meet the criteria that define a DLT in the dose-escalation phase of the study, enrollment in the expansion cohort(s) may be paused and the study data reviewed to determine whether additional monitoring or other action (such as alternate dose levels) should be evaluated prior to further enrollment.

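### Patients added to a Part 1 dose level after its 3+3 cohort face no numeric DLT limit, and their DLTs do not enter the written MTD definition

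*Protocol*

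**What the plan says.** **Adding patients.** Under Protocol 4.1.1, "the DESC may expand enrollment at doses below the current dose level as part of the dose-escalation process". The condition is response: "Additional patients may only be added at a lower dose level provided there is at least 1 patient who has achieved a PR" or better. "No more than 10 patients in total can be treated at any dose level unless" at least 3 of the 10 have responded. After Amendment 5, if 2 more patients respond, "additional patients will be treated at a dose patients have cleared the DLT period". None of these conditions contains a DLT count.

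**MTD.** Section 4.1.1 defines it as the highest level at which "none of the first 3 treated patients, or no more than 1 of the first 6 treated patients" has a DLT. The synopsis repeats this: "The MTD; therefore, is defined as the highest dose level at which none of the first 3 treated patients", with the same 1-of-6 alternative.

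**Rules that respond to toxicity.**
- Section 4.1.2 has the only cumulative DLT threshold (more than 30%). It applies to Part 2 and is permissive: "enrollment in the expansion cohort(s) may be paused and the study data reviewed".
- Section 6.5 halts enrolment "if any patient in Part 1 or Part 2 experiences a CTCAE Grade 5 AE, or 2 non-hematologic CTCAE Grade 4 AEs" if relationship to the drug cannot be excluded, or on one further GBS case. It stops the study on two further polyradiculopathy/GBS cases, or when at least 30% of patients have one specific non-hematologic event of Grade 4 or worse.
- Section 4.1.1 limits the next escalation step to 50% (Q3W) or 25% (QW) once a DLT is seen at a level.
- Section 7.3.1.2 has the DESC review safety at least monthly and set dose levels and the MTD from safety findings and DLTs. It gives no number.

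**Analysis.** Protocol 8.2.1 puts DLTs and the MTD first among the primary endpoints, 8.4 defines a DLT-evaluable set, and 8.6.1.1 promises a summary of all DLTs. The SAP defines only the safety set (4.1), lists DLTs without tabulating them (4.8.1, Dose-limiting Toxicities), and allows small dose levels to be combined (section 4). SAP 3.3 records that the trial ended before Part 1 was complete.

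**The concern.** A level with responses is the one most likely to be expanded, and it is a natural candidate for Part 2. The 3+3 stage rests on 3 to 6 patients and often passes a level that is too toxic. Patients added later are the best chance to find this out, yet the written MTD criterion stops counting before it reaches them.

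DLTs under 7.3.1.1 start lower than the triggers in 6.5. Grade 3 non-hematologic events, peripheral neuropathy from Grade 2 that is not GBS or polyradiculopathy, and prolonged cytopenia are all dose-limiting. A run of these at an expanded level would trip no count-based rule. What is at stake is the soundness of the stated MTD, part of the first primary endpoint, and the exposure of the added patients.

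**Working it through.** **Inputs.** The 3+3 steps, the MTD criterion and the cap of 10 come from Protocol 4.1.1, and the 30% figure from 4.1.2. The true per-patient DLT rate p is not in the documents; I assume 10% to 50%, with independent patients. The only design figure stated is the sample size, and 50 + 30 = 80 (8.3) reproduces. No operating characteristics are given.

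**1. What the wording permits.** A level at 1/6 that then has 4 DLTs in 4 added patients stands at 5/10 and still meets the criterion. Read literally, 0/3 followed by 7/7 (7/10) meets it too.

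**2. Passing 3+3.** P(pass) = (1−p)³ + 3p(1−p)⁵. At p = 0.40: 0.2160 + 0.0933 = 0.309.

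**3. Passing, then ending at 4 or more DLTs in 10 if filled.** 
P = (1−p)³ × P(Bin(7,p) ≥ 4) + 3p(1−p)⁵ × P(Bin(4,p) ≥ 3).
- p = 0.20: 0.512 × 0.0333 + 0.1966 × 0.0272 = 0.0171 + 0.0053 = 0.0224
- p = 0.30: 0.343 × 0.1260 + 0.1513 × 0.0837 = 0.0432 + 0.0127 = 0.0559
- p = 0.40: 0.216 × 0.2898 + 0.0933 × 0.1792 = 0.0626 + 0.0167 = 0.0793

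Dividing by P(pass) gives the figure for a level known to have passed.

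| True DLT rate | Passes 3+3 | Passes and ends ≥4/10 | Ends ≥4/10, given pass |
|---|---|---|---|
| 10% | 90.6% | 0.3% | 0.3% |
| 20% | 70.9% | 2.2% | 3.2% |
| 30% | 49.4% | 5.6% | 11.3% |
| 40% | 30.9% | 7.9% | 25.6% |
| 50% | 17.2% | 7.7% | 44.9% |

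**4. Stricter reading of the criterion.** Suppose a level with 6 or more patients must have at most 1 DLT in its first 6. The unconditional figure becomes (1−p)⁶p⁴ + 2 × 3p(1−p)⁵ × P(Bin(4,p) ≥ 3). At p = 0.40 this is 0.0012 + 2 × 0.0167 = 0.0346. For p = 0.20/0.30/0.40 the results are 1.1/2.6/3.5%.

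**5. A pause above 30%.** The smallest counts above 30% are 2 at n = 4–6 (2/6 = 33%), 3 at n = 7–9 (3/9 = 33%) and 4 at n = 10, since 3/10 is exactly 30%. Exact enumeration of the 2¹⁰ outcome sequences, checking after each added patient up to 10, gives:

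| True DLT rate | Pause, given pass | Passes, then pauses |
|---|---|---|
| 10% | 3.4% | 3.1% |
| 20% | 13.6% | 9.6% |
| 30% | 28.9% | 14.3% |
| 40% | 46.8% | 14.5% |
| 50% | 64.8% | 11.1% |

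At 40% the rule misses 100 − 46.8 = 53.2% of expanded levels. Of the levels it pauses, 61% at p = 0.30 and 45% at p = 0.40 would have ended at 3/10 or fewer if filled.

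**The case against.** The strongest reply is that the DESC already does this job. It meets at least monthly, sees every DLT, sets dose levels and the MTD, and is nowhere confined to the first six patients. Expansion is its own option. The Part 2 dose is a separate determination (8.2.1), and Part 2 cohort decisions draw on safety data to date (8.3). Exposure is limited too: at most 9 more escalation patients after Amendment 5 unless 2 more respond, 10 per level unless 3 respond, and individual withdrawal after a Cycle 1 DLT (6.4). On this view a numeric limit is a preference, and the proposed pause only returns the question to the same committee.

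Much of this stands. A reader might infer that DLTs in added patients go unmonitored, or that no mandatory rule reacts to them. The documents do not support that, given DESC review, 6.5 and the escalation-step limit. A reader might also take the conditional 25.6% at a 40% rate as the chance of a wrong MTD. It is not: the level must first pass 3+3, have met the response condition, be filled to 10, and be the highest level that passes.

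What does not fall is the textual point. The same committee works to fixed DLT limits in the 3+3 stage and has a 30% marker in Part 2. Only added Part 1 patients have no DLT figure, and the MTD definition as written leaves them out. Figure 2 is not visible to me and might show further thresholds, but the text of 4.1.1 sets out the procedure and the definition without any.

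**Conclusion.** The point holds in limited form, and it is minor. Part 1 allows response-driven growth of a level, no numeric DLT limit closes that level, and the written MTD criterion ignores patients beyond the first 3 or 6. The size is modest: 2.2/5.6/7.9% at true rates of 20/30/40% for passing and then ending at 4 or more of 10, or 1.1/2.6/3.5% on the stricter reading. Both rest on assumed rates, independence and filling to 10, and come before the response condition and the highest-passing-level condition.

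It would be tempting to conclude that an over-toxic dose was, or would have been, carried into Part 2. The documents do not support this: the Part 2 dose is a separate DESC decision, and the trial stopped before dose escalation was complete. For the same reason the enrolment rule now matters mainly as a design lesson. The reporting gap remains: listings sorted by dose level let a reader count DLTs, but they give no evaluable denominator for a primary endpoint.

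**What to change.** **Reporting (still applies).** Restore the DLT-evaluable set of Protocol 8.4 to SAP 4.1. In SAP 4.8.1 (Dose-limiting Toxicities), add a table of DLTs as n/N per dose level and schedule over that set, counting all added patients and not pooling levels into ranges. Cost: one set definition and one table, with no new data.

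**Design (4.1.1 and synopsis, cross-referenced in 6.5).** Suggested text: *The MTD is judged on all DLT-evaluable patients at a level; a level at which more than 30% have had a Cycle 1 DLT does not qualify. Once a level is expanded beyond its 3+3 cohort, enrolment at that level pauses when this proportion is exceeded (2 of 4–6, 3 of 7–9, 4 of 10; beyond 10, more than 30%) until the DESC records a decision to resume or close it.* The 30% figure is borrowed from 4.1.2, but that rule is discretionary and covers the whole treatment period. The 2-of-6 limit agrees with the existing 3+3 limit.

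**Cost.** An expanded level would be falsely paused in 3–14% of cases at true rates of 10–20%. A pause holds one level, not the trial. At a true 40% the mean number of patients spared per expanded level is 1.41 if each outcome is known before the next patient is treated, 0.95 if one more patient has been treated by then, and 0.60 if two have. These figures hold only if enrolment does not resume. Hematologic DLTs need 6 to 8 weeks to confirm (7.3.1.1), so they would count later still.
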